6.4.3.2 Eye comfort index

This questionnaire is designed to measure ocular surface irritation using Rasch analysis to produce estimates on a linear interval scale (scores: 0–100). Similar to the index for ocular surface diseases, the Ocular Comfort Index (OCI) assesses symptoms. The OCI contains six items that focus on discomfort associated with the ocular surface. Each of these questions has two parts, which separately inquire about the frequency and severity of symptoms. [44]See Appendix 14.1 Eye comfort index

The evaluator will give the questionnaire to the subject and allow them to answer it calmly without any pressure or coercion. They will only assist them if they have difficulty understanding any of the questions.

Ocular surface stains

- *Lissamine green staining* .

A drop of topical anesthetic will be instilled into the conjunctival fornix. A second drop will then be applied to the tip of the lissamine green strip and allowed to run into the fornix. It is essential to rapidly assess the staining, sequentially, first in the OD and then the OS, so that the observed patterns are equally bright. [19]See Appendix 14.2 Oxford Scale

- *Fluorescein staining*.

A drop of topical anesthetic will be instilled in the conjunctival fornix. A second drop will then be applied to the tip of the fluorescein strip and allowed to run into the fornix. It is essential to rapidly assess the staining, sequentially, first in the OD and then the OS, so that the observed patterns are equally bright. This assessment will be performed using a cobalt blue filter. [19]See Appendix 14.2 Oxford Scale

For both stains, the value obtained according to the Oxford scale will be recorded in the CRF.

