5.2.1.1 Pharmacokinetics in the eyeball

Route of administration: Ophthalmic.

Release: immediate.

Absorption: No absorption of HS through the cornea has been reported when applied to the ocular surface. Pharmacokinetic studies conducted in patients with dry eye showed that the HS solution reached its maximum concentration within 10 minutes and is widely distributed across the ocular surface.

Metabolism: It is biotransformed by hyaluronidases.

Elimination: It is eliminated from this compartment through the lacrimal sac and tear duct without intraocular absorption, in approximately 45 minutes. [30]Based on the results of preclinical research in rabbits conducted by Laboratorios Sophia SA de CV, the ocular half-life correlates with the volume of the formula.

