6.3 Intervention

6.3.1 Treatments administered

6.3.1.1 Treatment under study

- **PRO-165**
 - Active ingredients (lubricant): sodium hyaluronate 0.2%
 - Pharmaceutical form: Ophthalmic gel
 - Prepared by: Laboratorios Sophia , SA de CV
 - Dosage: One drop of gel, 4 times a day during the waking period, in the fornix of the right eye.

- Formulation description: Clear gel, free of visible particles.
- Packaging description: Sterile multi-dose tube, low-density polyethylene and aluminum polylaminate with high-density polyethylene cap.

Table 4Qualitative -quantitative formulation of PRO -165

Agent type	Amount mg/ mL	Function
Sodium hyaluronate	2.0	Active ingredient
Chondroitin sulfate	Not shown	Viscosant
Polyoxylated Castor Oil 35	Not shown	Solubilizer
Polyethylene glycol 8000¹	Not shown	Cosolvent
Eddate disodium dihydrate	Not shown	Chelating agent
Cetrimide	Not shown	Conservative
Glycerin	Not shown	Osmoregulator
Sodium hydroxide	Not shown	pH adjustment
Homopolymer carbomer type B²	Not shown	Gelling agent
Polycarbophil³	Not shown	Gelling agent
Water for the preparation of injectables cbp⁴	Not shown	Vehicle

Qualitative and quantitative formulation of the investigational product PRO-165. The concentration of the active ingredient is shown, as well as the substances that act as additives. (1) Synonym of Carbowax® (2) Synonym of Carbopol® 974P NF Polymer, USP (3) Synonym of Noveon® AA-1 Polycarbofil, USP (4) as much as is sufficient for

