6.4.3.1 Visual capacity

Visual acuity (VA) is a test of visual function. Spatial visual acuity is the ability to distinguish separate elements of an object and identify them as a whole. It is quantified as the minimum angle of separation (located at the nodal point of the eye) between two objects that allows them to be perceived as separate objects.

Snellen notation is described as the distance at which the test is performed divided by the distance at which the letter is vertically equivalent to 5 minutes of arc. Thus, at 6 meters, a letter 6/6 (20/20) is equivalent to 5 minutes of arc, a letter 6/12 (20/40) is equivalent to 10 minutes, and a letter 6/60 (20/200) is equivalent to 50 minutes. The Snellen fraction can also be expressed as a decimal (i.e., 20/20 = 1 and 20/40 = 0.5). [43]

VA will be assessed at baseline, without refractive correction, using the Snellen chart. This chart will be placed in a location with adequate natural or artificial lighting and at a distance of 3 m from the subject being assessed. Visual acuity will be measured in each eye, starting with the right eye (RE),

asking the subject to keep both eyes open and using an occluder to cover the left eye (LE); the subject will read aloud the lines indicated by the evaluator. The evaluator will record the smallest line of letters visible as the RE VA in the clinical record. The LE is then assessed using the same method.

The subject's best refractive correction will then be performed, and the examination will be repeated using the obtained refraction. This result will be reported as CV, entered as a fraction in the clinical record and on the Case Report Form (CRF), and will also be entered as a decimal on the CRF. By definition, the CV cannot be less than the VA.

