6.4.3.5 Intraocular pressure

Tonometry is the objective measurement of IOP, based primarily on the force required to flatten the cornea or the degree of corneal indentation produced by a fixed force. Goldman tonometry, based on the Imbert-Fick principle, is considered the gold standard for IOP measurement.

[43]Tonometry is performed after instillation of a drop of topical anesthetic (tetracaine 0.5%), fluorescein, and the use of a cobalt blue filter (after evaluating corneal surface staining). These measurements are recorded in the clinical record and on the CRF.

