6.4.3.7 Tear film break-up time

One of the first aspects of the tear film to change when there is a change in the ocular surface is its stability. In general, if the corneal or conjunctival surface is damaged, it is unlikely that a stable tear film can be maintained.

The most common method for assessing tear film stability is fluorescein-based TRL. Once fluorescein is instilled, the patient is asked not to blink using the cobalt blue filter. The fluorescein-stained precorneal layer will shift to less fluorescent or non-fluorescent regions. The time elapsed from the last blink until these regions appear is the TRL. It is reported in seconds in the clinical record and on the CRF.

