6.6.1 Sample size calculation

There are no references on the calculation of the sample size in phase I studies, and the formulation of Humylub Ofteno® has not reported any adverse events in its periodic safety reports. Therefore, it was considered appropriate to base the calculations on previous phase I studies conducted by Laboratories . Sophia , SA de CV [45, 46, 47, 48].

The calculation was based on the adverse event presentation reported by Christ T., in a randomized, single-blind, parallel-group controlled clinical trial evaluating the efficacy and tolerability of a 5% dexamphenol ophthalmic gel versus a 5% panthenol ointment in 48 subjects with corneal erosion, UV-induced keratoconjunctivitis, or similar conditions. The intervention consisted of applying 1 cm of the gel and ointment for 4 and 3 days, respectively.[49]

The percentage of good tolerance reported with the gel was 25%, so it is expected that no more than 10% of subjects will report poor tolerance with the formulation proposed in this protocol.

The sample size was calculated using the formula for proportions

$$n = p (1 - p) \left(\frac{Z_{1-\alpha} + Z_{1-\beta}}{p - p_0 - \delta} \right)^2$$

With a statistical confidence of 95% corresponding to type I error, equal to 1.96, with a power of 90%, corresponding to type II error, equal to 0.84.

According to the previous calculation, the result is 26 subjects, which was increased by 20% to account for probable losses. The total required sample size is **32 subjects** . Therefore, each group will consist of 16 subjects, each of whom will contribute an eye to the analysis.

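### The planned tests of the secondary ocular variables adjust for neither the baseline value nor the untreated left eye, although the left eye is examined at least for staining and visual capacity

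*Protocol*

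**What the plan says.** **Treatment.** Protocol 6.3.1.1 gives the regimen as "One drop of gel, 4 times a day during the waking period, in the fornix of the right eye", and 6.3.1.2 repeats it for the reference gel. The left eye is untreated in both arms.

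**Left-eye examination.**
- Staining (text under Ocular surface stains, after 6.4.3.2): both dyes are read in both eyes, "It is essential to rapidly assess the staining, sequentially, first in the OD and then the OS".
- Visual capacity (6.4.3.1): "Visual acuity will be measured in each eye", and "The LE is then assessed using the same method". The corrected result goes into the CRF as a fraction and as a decimal.
- Intraocular pressure (6.4.3.5): "These measurements are recorded in the clinical record and on the CRF", with no eye named.
- Tear break-up time (6.4.3.7): "It is reported in seconds in the clinical record and on the CRF", again with no eye named.

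All four are scheduled at baseline (or carried over from screening), Visit 1 and the Final Visit.

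**Analysis.** Protocol 6.6.1 has 16 subjects per group, "each of whom will contribute an eye to the analysis". For quantitative variables, protocol 8.3.1 plans Kruskal-Wallis (also naming Student's t) between groups and Wilcoxon within groups. The SAP plans Mann-Whitney and Wilcoxon. SAP Table 2 assigns these to intraocular pressure, visual capacity and tear break-up time, all labelled as changes. It assigns chi-square or Fisher, with McNemar if applicable, to both stains. No analysis section names a covariate or uses the left eye as a control. Adverse-event reporting does consider all eyes of randomised participants.

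**The concern.** Two sources of information are left out of the comparisons.

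The first is the baseline value of the treated eye. At most it enters through a change score, which fixes its coefficient at 1 instead of estimating it.

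The second is the fellow eye. It shares the subject, examiner, room and day with the treated eye but receives no gel. Both arms receive a gel and protocol 5.6.1 judges placebo not feasible, so the left eye is the only concurrent untreated comparison in the trial. Read as a before/after test, the within-arm Wilcoxon attributes to the product anything that differs between visits.

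At stake is the precision and interpretability of the objective ocular safety measures with 16 eyes per arm.

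**Working it through.** The plan states no precision or power for the ocular variables, so there is no figure to reproduce. Its sample-size calculation concerns a tolerance proportion and does not bear on this point.

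**Inputs.** From the documents: 16 per arm, alpha 0.05, one treated eye per subject. Assumed, because the documents give nothing: normal data, a between-arm effect of 0.8 SD, and three correlations:
- *v*: same eye, baseline to follow-up; 0.5 to 0.7.
- *r*: between eyes at the same visit; 0.3 to 0.8.
- *c*: between eyes across visits; 0.3 to 0.6.

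**Step 1: using baseline.** Variances are relative to the raw follow-up value (= 1).
- Change score: 2(1 − *v*) = 2 × 0.5 = 1.00 at *v* = 0.5; 2 × 0.3 = 0.60 at *v* = 0.7.
- Baseline ANCOVA: 1 − *v*² = 1 − 0.25 = 0.75; 1 − 0.49 = 0.51.

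Simulated power, in the order *v* = 0.5 then 0.7:
- Mann-Whitney on raw follow-up values: about 56% at either.
- Mann-Whitney on change: about 56%, then about 78%.
- Baseline ANCOVA: about 70%, then about 86%.

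**Step 2: adding the same-visit left-eye value to baseline ANCOVA.** Residual variance = 1 − (*v*² + *r*² − 2*vrc*)/(1 − *c*²). For example, *v* = 0.5, *r* = 0.8, *c* = 0.4 gives 1 − (0.25 + 0.64 − 0.32)/0.84 = 0.32. The change in power is from 4,000 simulated trials per row:

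| *v* | *r* | *c* | Residual variance, baseline only | Baseline + left eye | Change in power (points) |
|---|---|---|---|---|---|
| 0.7 | 0.3 | 0.3 | 0.51 | 0.50 | about 0 |
| 0.7 | 0.5 | 0.5 | 0.51 | 0.48 | +1 |
| 0.7 | 0.7 | 0.5 | 0.51 | 0.35 | +10 |
| 0.7 | 0.8 | 0.6 | 0.51 | 0.28 | +12 |
| 0.5 | 0.5 | 0.5 | 0.75 | 0.67 | +3 |
| 0.5 | 0.5 | 0.3 | 0.75 | 0.62 | +7 |
| 0.5 | 0.7 | 0.4 | 0.75 | 0.45 | +20 |
| 0.5 | 0.8 | 0.4 | 0.75 | 0.32 | +25 |

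The gain is material only when the eyes agree more closely within a visit than across visits (*r* above *c*), that is, when they share visit-level variation. Where *r* = *c* it is negligible.

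**Step 3: treated-minus-fellow contrast.** Its variance relative to the treated eye alone is 2(1 − *r*): 2.0, 1.4, 1.0, 0.6 and 0.4 at *r* = 0, 0.3, 0.5, 0.7 and 0.8. It loses precision below 0.5, breaks even at 0.5 and gains above. For changes from baseline the relevant correlation is that of the changes. If both eyes have the same *v* and *c*, this is (*r* − *c*)/(1 − *v*). With *v* = 0.7 and *r* = *c* = 0.5 it is 0, and the contrast doubles the variance.

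**The case against.** **An optional covariate in an exploratory phase I study is a choice, not an error.** This stands. The point concerns efficiency and interpretation of secondary variables and should be ranked accordingly.

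**A reader might infer that low precision here favours the sponsor's claim, since the gel is called safe and tolerable when no difference is found.** The documents do not support that. In protocol 8.3.1 and the SAP the rule covers the primary variables, which are adverse events and the comfort index. All the variables discussed here are secondary and outside it.

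**A reader might set right-eye Mann-Whitney on raw values (about 56%) against fellow-eye ANCOVA and credit the whole difference to the left eye.** That is the wrong comparator. The SAP labels these variables as changes, and much of the gain comes from baseline adjustment alone.

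**Staining.** The SAP tests it by chi-square or Fisher and McNemar, so the Mann-Whitney and Wilcoxon argument does not describe it. Grades in healthy eyes are probably mostly zero (an assumption), so little gain is likely. The comfort index asks about both eyes together and cannot use a left-eye control.

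**The left eye may not be a clean control.** Protocol 5.2.1.1 says "No absorption of HS through the cornea has been reported when applied to the ocular surface", which concerns hyaluronate only. It does not cover the cetrimide in PRO-165, the carbomer comparator, or gel put in the wrong eye. The same-visit left-eye value is also measured after randomisation. These are reasons to keep that analysis supportive.

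**Left-eye data may not exist for every variable.** The eye is unstated for intraocular pressure and tear break-up time, and CRF capture by eye is unstated for staining. Nor is the left eye wholly unused, since adverse-event reporting considers all eyes. What is missing is its use as a control.

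**Conclusion.** The point holds as a minor improvement. The treated and untreated eyes are clearly defined, the left eye is examined at least for staining and visual capacity, and the planned ocular tests adjust for neither baseline nor fellow eye.

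The firmer part is baseline adjustment: power of about 70–86%, against about 56–78% for Mann-Whitney on change. The left-eye covariate adds about 0 to 12 points at a visit-to-visit correlation of 0.7, and about 3 to 25 points at 0.5. All these figures rest on assumed normal data, a 0.8 SD effect and correlations that the documents do not report. Decimal visual capacity in subjects selected for 20/30 or better may depart from the normal model.

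The limit of an uncontrolled before/after test does not depend on those correlations. The analysis cannot be said to raise precision for every ocular variable, and it lends no support to a criticism of the formal safe-and-tolerable rule.

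**What to change.** 1. **Main comparison.** In protocol 8.3.1 and SAP Table 2, compare arms on intraocular pressure, tear break-up time and decimal visual capacity by ANCOVA, or rank ANCOVA, of the treated-eye value adjusted for its baseline.
2. **Data capture.** State which eye or eyes are measured for intraocular pressure and tear break-up time, and record all ocular findings by eye in the CRF.
3. **Supportive analysis.** Where the left eye is recorded, prespecify a model that adds its same-visit value as a covariate.
4. **Within-arm description.** Report treated-minus-fellow change in each arm alongside the Wilcoxon, as description.
5. **Stated limits.** Say in the SAP that the left-eye analyses assume neither gel affects the left eye, and that the treated-minus-fellow contrast is less precise if the between-eye correlation of the analysed quantity is below 0.5.

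**Cost.** CRF fields by eye, a little more code, and one or two degrees of freedom. No extra subjects or visits are needed. If left-eye pressure or break-up time is not now measured, adding it would lengthen the examination; otherwise confine items 3 and 4 to the variables that have left-eye data.

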6.4.3.4 Presence of adverse events

The management of AEs will be carried out according to what is described in section 9.3 Adverse events

The IP will record any AEs presented by the study subjects in the corresponding section of the CRF, in addition to mentioning them in their essential document.

The IP must perform a complete ophthalmologic examination of the ocular surface, anterior segment, and posterior segment. Any pathological changes found must be reported in accordance with the AD management guidelines.

6.4.3.5 Intraocular pressure

Tonometry is the objective measurement of IOP, based primarily on the force required to flatten the cornea or the degree of corneal indentation produced by a fixed force. Goldman tonometry, based on the Imbert-Fick principle, is considered the gold standard for IOP measurement.

[43]Tonometry is performed after instillation of a drop of topical anesthetic (tetracaine 0.5%), fluorescein, and the use of a cobalt blue filter (after evaluating corneal surface staining). These measurements are recorded in the clinical record and on the CRF.

6.4.3.6 Vital signs

The vital signs to be assessed (HR, RR and SBP) may be measured by an assistant duly designated in the center's organization and the delegation of responsibilities. The technique to be used for HR and RR will be counting repetitions in one minute by direct auscultation with a stethoscope.

SBP should be measured after 5 minutes of rest on the left arm. The instrument may be manual or automatic, as the PI deems appropriate. All measurements must be performed under equal conditions. Three measurements will be taken, with a minimum interval of 5 minutes between measurements, and recorded in the patient record. The average will also be recorded on the grade and the CRF.

6.4.3.7 Tear film break-up time

One of the first aspects of the tear film to change when there is a change in the ocular surface is its stability. In general, if the corneal or conjunctival surface is damaged, it is unlikely that a stable tear film can be maintained.

The most common method for assessing tear film stability is fluorescein-based TRL. Once fluorescein is instilled, the patient is asked not to blink using the cobalt blue filter. The fluorescein-stained precorneal layer will shift to less fluorescent or non-fluorescent regions. The time elapsed from the last blink until these regions appear is the TRL. It is reported in seconds in the clinical record and on the CRF.

6.4.3.8 Pregnancy test

This refers to the performance of a rapid pregnancy test in all women of childbearing age who wish to enter the study. By childbearing age, we mean women who have not experienced menopause. For the purposes of this study, menopause is defined as 12 months from the last menstrual period in women over 40 years of age or who have undergone a hysterectomy or bilateral oophorectomy. Women of childbearing age using contraceptive methods, including bilateral tubal obstruction , must undergo a pregnancy test. This test will be performed by the PI or a designated team member according to the instructions for the device provided by the sponsor. When applicable, the performance, result, and date must be recorded on the CRF. If not applicable, the reason must be noted.

6.4.3.9 Laboratory tests

The PI will generate the order for the BH, QS, and LFT studies, to be performed by the clinical laboratory designated by the sponsor. The clinical laboratory will provide the PI with the results for evaluation and recording. The normal parameters to be considered will be the ranges established by the laboratory; however , the PI's clinical judgment will prevail in determining whether the results are normal or abnormal.

6.4.4 Time of measurements

Measurements of the primary and secondary outcome variables will be performed and evaluated for each visit, according to the following:

Baseline Visit / Day 0.

Some of these measurements will be performed at the screening visit to complete the eligibility criteria (see Study schedule and diagram), at the discretion of the PI, and if no more than 10 days have passed, they may be taken to complete the baseline visit data.

1. Visual capacity.
2. Intraocular pressure.
3. Eye comfort index
4. Ocular surface evaluation
 - a. Includes stains
 - b. TRL
5. Adverse event evaluation.
6. Vital signs.
7. Evaluation of laboratory test results

Visit 1 / Day 5.

It can be done in a period of \pm 2 days in relation to day 5 of application.

1. Visual capacity.
2. Intraocular pressure.
3. Ocular surface evaluation
 - a. Includes stains
 - b. TRL
4. Vital signs.
5. Adverse event evaluation.

Final Visit / Day 11.

It can be done in a period + 1 day in relation to the 11th day of the start of application, not before the 11th day since the 10 days of application would not be met.

1. Visual capacity.
2. Intraocular pressure.
3. Eye comfort index
4. Ocular surface evaluation
 - a. Includes stains
 - b. TRL
5. Vital signs.
6. Evaluation of adverse events.

Safety Call / Day 13.

It can be carried out within a period of \pm 1 day in relation to the 13th day from the start of application.

1. Ask about the presence of any adverse events.
2. Evaluation of laboratory test results

6.5 Study schedule and diagram

Procedures	Scrutiny	Baseline Visit	Visit 1	Final Visit	Security Call
	Day 0 - X to	Day 0	Day 5 ± 2	Day 11 at + 1	Day 13 ± 1
CI Signature	X				
Medical record	X				
Ophthalmological clinical history	X				
Laboratory sample collection	X			X	
Laboratory Test Review		X			X
Pregnancy test	X			X	
Eligibility criteria	X	X ^b			
Assignment		X			
Delivery of intervention		X ^c			
Return of intervention				X	
Adherence assessment			X	X	
Adverse events			X	X	X
Intraocular pressure	X	X ¹	X	X	
Visual capacity	X	X ¹	X	X	
TRL	X	X ¹	X	X	
Ocular surface stains	X	X ¹	X	X	
Vital signs	X	X ¹	X	X	
Eye Comfort Index		X		X	
Submission of the subject's diary		X	X		
Return/Evaluation of the Subject's Diary			X	X	
Return and Evaluation of the quality questionnaire				X	
Subject continuity assessment			X		

^aThe screening visit may be up to 10 days prior to the baseline visit; if this is exceeded, the subject will not be allowed to enter.

^bThese criteria will be completed with the results of the laboratory tests and those collected during the scrutiny visit.

^cThe instruction will be given to start the application the following day.

¹They can be taken from the screening visit, as long as no more than 10 days have passed; it is the IP's prerogative to measure them again at the baseline visit.

